data will be supplemented with qualitative data from the meaning making session and storytelling content, for those who participate.

Aim 3 (Community Intervention): Prepare an exhibit of art made by patients and stories of their experiences and evaluate whether this exhibit impacts stigma regarding chronic pain and opioid use in the broader population (audience). *Hypothesis 6: Laypersons viewing photographs of the art paired with patients' descriptions of their art and the artmaking process, will lessen stigma towards people with chronic pain and OUD/opioid misuse.* Laypersons who view the exhibit and who complete a retroactive pre-post survey will self-report lessened stigma towards persons with chronic pain and OUD/opioid misuse through positive appraisal of the artists.

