Check-in Texts & Calls	The Study Coordinator will text all patients one (1) month after the in-person workshop and every one (1) month thereafter for a total of four (4) connection points to assess any barriers to at-home engagement; for those patients who do not respond to texts, the Study Coordinator will complete phone calls and document in Redcap	
 • Question asking whether patients used the art kits in the past month • Documentation of any barriers • Brief qualitative data
Meaning Making Session	All patients will be invited to join a two-hour virtual meaning making session	
 • Rich qualitative data of their experience of the art kits and solo repetitive artmaking
Exhibit	Exhibit viewers (laypersons) will complete an online post-survey via QR code that captures reactions before/after viewing the exhibit	
 • Short set of stigma questions to be developed

Most data will be collected online, via an online survey that automatically populates into a password protected spreadsheet. The Patient Advocate or Study Coordinator will collect all paper surveys during routine treatment at [name] and provide them to the Study Coordinator, who will clean and manually input the data.

Data Analysis:

Analysis will be conducted through a mixed-methods approach. Quantitative analysis to test hypotheses 2-5 will be led by [name], Biostatistician, who will report changes from pre- and post-surveys on all the measures provided to patients and exhibit viewers. For bivariate analyses, he will use paired t-tests. For multivariate analyses, he will employ control variables from baseline, such as demographic variables, and conduct linear regressions. Qualitative analysis to test hypotheses 1-5 will be led by the co-PI, who will code all qualitative data collected from patients (open-ended questions in all surveys, transcript from the meaning making session) to

surface themes that can provide phenomenological or experiential data. Drs. [name] and the co-PIs will collaborate to develop a final report that includes both quantitative and qualitative data.

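### As worded, H6 lets favourable appraisal of the artists count as lessened stigma towards the whole population, and its single post-viewing survey cannot separate real change from recall or courtesy bias

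*Combined protocol and SAP*

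**What the plan says.** Aim 3 (1. Specific Aims) sets out to evaluate whether the exhibit affects stigma in the broader population. Hypothesis 6 is that viewing photographs of the art, with the patients' descriptions, "will lessen stigma towards people with chronic pain and OUD/opioid misuse". The criterion follows. The group it covers is given as "Laypersons who view the exhibit and who complete a retroactive pre-post survey". What is predicted of this group is that its members "will self-report lessened stigma towards persons with chronic pain and OUD/opioid misuse through positive appraisal of the artists".

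The Exhibit row of the data collection table (3. Research Design and Methods) says that viewers "will complete an online post-survey via QR code that captures reactions before/after viewing the exhibit". Its entry for the measure is "Short set of stigma questions to be developed".

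The Data Analysis paragraph of the same section says that the biostatistician "will report changes from pre- and post-surveys on all the measures provided to patients and exhibit viewers". The general method it gives is: "For bivariate analyses, he will use paired t-tests". It assigns quantitative testing to hypotheses 2 to 5 and qualitative testing to hypotheses 1 to 5. H6 is in neither list. No number of viewers, threshold for success or comparison group of non-viewers is given.

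**The concern.** Two features of the H6 criterion make a favourable finding easier to reach than the hypothesis warrants.

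- **Target.** The hypothesis is about a population; the criterion refers to the people whose work is on show. The In-Person Workshop paragraph makes displaying art voluntary, so the exhibitors are a self-selected part of a pilot of about 40 patients. Thinking well of them, after seeing their art and reading their accounts, is not in itself a changed attitude to everyone with chronic pain and OUD/opioid misuse.
- **Timing.** No rating is taken before viewing. The viewer reconstructs the earlier attitude on the same form that records the present one, after seeing patients' art and stories whose hoped-for effect is easy to guess.

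At stake is the Aim 3 conclusion. Appraisal of a few volunteers, or a recalled difference, could be reported as an observed reduction in stigma brought about by the exhibit.

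**Working it through.** There is no H6 figure in the plan to reproduce. The check sets the texts side by side, then illustrates how far bias could matter.

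**1. Target.** The secondary focus in the opening of 1. Specific Aims, and H6 itself, both name the population. The criterion names the population as the object of stigma but brings in the artists as the means by which lessened stigma shows. The data collection table does not settle the matter: it calls the items stigma questions but leaves them to be written. Nothing in the plan requires an item about the population, and nothing prevents an artist item from being scored as the H6 result.

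**2. Timing.** The Aim 3 text calls the survey retroactive, and the Exhibit row describes a single post-survey covering both time points. The two places agree. For contrast, the At-Home Artmaking paragraph asks patients to complete their first survey directly before starting a kit, so the patient hypotheses do have a prospective first rating.

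**3. What the change score estimates.** Let B and A be a viewer's true stigma before and after viewing. Let r be the amount by which recall overstates B, and c the amount by which courtesy understates A. Then

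recalled before − reported after = (B + r) − (A − c) = (B − A) + (r + c).

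Only the sum is observed. One post-viewing form gives no way to estimate r + c, and the plan describes no non-viewer sample that could.

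With an entrance rating, which may carry its own courtesy e, the score is (B − e) − (A − c) = (B − A) + (c − e). Recall error drops out, but any courtesy at exit beyond that at entrance remains.

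**4. Illustration of size.** All of these inputs are assumptions:

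- no true change (B = A on average) and one form per viewer;
- mean bias b = r + c, in SDs of the change score, in the favourable direction;
- a two-sided 5% paired t-test, which is the plan's general bivariate method and is not named for H6;
- n viewers, a number the plan does not state.

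P(favourable significant result) = 1 − F(t₀.₉₇₅,ₙ₋₁), where F is the noncentral t distribution with n − 1 degrees of freedom and noncentrality b√n.

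- n = 50, b = 0.2: noncentrality 0.2 × √50 = 1.414, critical value 2.010, probability 28%.
- n = 100, b = 0.2: noncentrality 0.2 × 10 = 2.0, critical value 1.984, probability 51%.

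| Viewers (assumed) | b = 0 | b = 0.1 | b = 0.2 | b = 0.3 |
|---|---|---|---|---|
| 30 | 2.5% | 8% | 18% | 36% |
| 50 | 2.5% | 10% | 28% | 55% |
| 100 | 2.5% | 17% | 51% | 84% |

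Any fixed favourable bias is more likely to reach significance as n grows, so surveying more viewers does not cure it.

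**The case against.** A reader might infer that this design cannot show anything about stigma. The documents do not support that. The retroactive design is openly declared, the criterion promises only that viewers will self-report a change, and the stigma question is a secondary focus of an exploratory pilot. A retrospective rating is weak evidence of perceived change, but it is evidence. This part of the objection stands.

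A reader might also infer that appraisal of the artists is fixed as the measure. It is not. The clause can be read as the expected route by which stigma falls, and the unwritten items are described as stigma questions. The artists also belong to the stigmatised group, so appraising them is closer to stigma than liking pictures would be. This also stands, but it leaves the difficulty in place: a criterion with two readings, one of which substitutes a few volunteers for the population, does not ensure that the named outcome is measured.

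The percentages are open to challenge too. The shift, its direction and the number of viewers are all assumed. H6 carries no significance criterion, unlike H2 to H4. They show how such a bias would act, not how large it is here.

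Finally, an entrance survey is not a clean remedy. It may sensitise viewers, it leaves courtesy at exit in place, and it yields a smaller, self-selected linked sample. That is a fair reason not to make it the main analysis.

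**Conclusion.** The point holds in limited form. Two facts rest on the text alone: the only stated criterion ties lessened population stigma to appraisal of the artists, and both ratings are given after viewing with no comparison group described. It follows that H6 as written does not ensure that stigma towards the named population is measured, and that recall or courtesy bias cannot be separated from real change. The survey can support a statement about self-perceived change among viewers who respond. It cannot support an observed reduction in stigma caused by the exhibit.

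The size is not determinable from the plan. The range of 17% to 84% for 100 viewers depends wholly on the assumed bias of 0.1 to 0.3 SD, the assumed viewer number and a test not named for H6. It should not be read as the false-positive rate of this study.

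**What to change.** 1. In 1. Specific Aims, Aim 3, define the H6 outcome as the change in items about people with chronic pain and OUD/opioid misuse in general.
2. Write the stigma items still to be developed for the Exhibit row of the data collection table to match that definition.
3. Report appraisal of the artists as a separate descriptive result, not as evidence of lessened stigma.
4. State that the retroactive survey supports only a conclusion about self-perceived change among responding viewers, and not an observed reduction in stigma caused by the exhibit.
5. Optionally, offer the same items by QR code at the entrance, linked to the later form by a code the viewer makes up, as a supporting analysis.

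Items 1 to 4 are wording changes with no added data collection, because the questions are not yet written. Item 5 costs a second form. Its downsides are a smaller, self-selected linked sample and possible sensitisation of viewers, and it does not remove courtesy from the later rating.

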2. SIGNIFICANCE

Chronic pain is extremely prevalent in the United States with approximately 20-21% or over 50 million adults reporting pain most or every day.^{1,2} Chronic pain can result in depression,^{3,4} anxiety,⁵ and isolation,^{6,7} among other negative affective outcomes.⁸ Many people who experience chronic pain have at some point in their medical journey been prescribed opioids,⁹ and many more have been found to misuse/overuse these pain medications: as of 2019, 6-7 million adolescent and adult Americans were diagnosed with OUD¹⁰ and, based on the 2021 National Survey on Drug Use and Health, 9.2 million people reported misusing opioids in the past year.¹¹ The cost of opioid misuse and OUD is estimated at \$11 billion in annual hospital costs¹² and totals an estimated \$1.02 trillion when including loss or reduced quality of life.¹³ It is therefore clear that solutions – and particularly low-cost solutions – to chronic pain are needed that can support patients with chronic pain and OUD/opioid misuse in managing their pain.

Art therapy is well-regarded as a cost-effective tool to minimize pain in individuals experiencing chronic pain.¹⁴⁻¹⁶ Practices that incorporate art into psychotherapy can support patients' self-understanding of their experience through full mind-body intervention.^{17,18} Outcomes of art therapy practice with patients experiencing chronic pain include: changes in physical symptoms,¹⁹⁻²² changes in psychological symptoms,²³⁻²⁸ and changes to social interactions such as increased socialization,²⁹ new relationships,³⁰ and improved communication.³¹ Specifically, the use of artistic practice as distraction from pain is useful for mitigating pain.³²⁻³⁴ Art therapy has been used in clinical settings to treat substance use disorders including OUD for 70 years with demonstrated success particularly in supporting detox and helping patients understand their relationship to substances.³⁵⁻⁴⁰ However, there remains a dearth of literature on treatment outside clinical treatment settings or to assess the utility of art therapy in mitigating the experience of chronic pain in patients with OUD.⁴¹

Since self-management is understood to be critical to chronic pain treatment,^{42,43} art-based solutions that allow patients to self-manage their symptoms outside of the clinical context are of particular interest. For instance, mandala creation, which is repetitive and can promote mindfulness, is often used in art therapy and in one study was shown to mitigate pain and anxiety in pediatric patients experiencing procedures that caused acute pain.⁴⁴ However art therapy is overwhelmingly offered in formal contexts with professional art therapists, and does not often provide options that patients can use on their own, away from clinical settings.

3. RESEARCH DESIGN AND METHODS

Overview:

The proposed pilot is an exploratory evaluation of whether repetitive artmaking in home environments is acceptable for chronic pain self-management in individuals with OUD/opioid misuse, and whether self-driven repetitive artmaking can offer respite from pain, depression, and anxiety, and improve social connectivity. The study will recruit approximately 40 individuals living with chronic pain with an OUD diagnosis or opioid misuse from a Montefiore-led methadone clinic, [name]. The Principal Investigators (PIs) will collaborate with an Art Therapist to develop three (3) simple art kits. Patients will participate in an in-person art workshop, to be held in English with the support of a Spanish translator, and complete pre- and post-surveys assessing in-the-moment pain, anxiety, depression, and social connectivity. Patients will be given all three (3) kits to take home and offered financial incentives to complete the same pre- and post-surveys and art kits at home up to four (4) times within a four-month period to assess real-world adoptability and efficacy. The art kits will not include any visible information about Montefiore or the study in the front of the packets; paper versions of the survey will be enclosed within the kits, to support confidentiality. All patients will be invited to a virtual meaning making group to capture qualitative feedback. The study staff will not share the names of patients with anyone outside the core research team – the co-PIs, Study Coordinator, Patient Advocate, Biostatistician, Art Therapist, and Photographer and Exhibit Coordinator. All patients will be invited to have their art photographed and share their experience of the artmaking process and how it relates to their chronic pain and opioid use. Photographs and stories will be shared on the Montefiore campus as an art exhibit, and the layperson audience will be surveyed to assess any resultant alteration in feelings of stigma toward the population of those living with chronic pain and OUD/opioid misuse. Patients who share their artwork will be able to decide if they want their name (or a portion of their name) or a pseudonym to be included in the exhibit alongside their artwork, or if they would like to maintain anonymity.

Implementation:

In-Person Workshop: [name], an Art Therapist, will lead three (3) two-hour in-person workshops at [name], with all patients required to attend one (1) in-person workshop as part of this study. Spanish translation will be available at all workshops. The purpose of these workshops are twofold: they will gather patient characteristic data (demographics, Pain Catastrophizing Survey, questions on experience with art and openness to mindfulness) and orient patients to the use of the art kits available to them to take and use at home. The art therapist will develop three (3) repetitive artmaking kit options and will develop enough for patients to leave the workshop with one of each kit. Preliminary options include mandala painting and macramé, with the final kits to be developed during the planning phase in partnership with the IMPOWR-ME Community Leadership Board. As previously stated, the art kits will be compiled to minimize visual identification from others that they are part of a research study, with all survey materials asking sensitive questions buried in the middle of the packet. At the start of the in-person workshop, the PI will orient patients to the pilot goals and activities, answer all questions, collect consent forms, and provide the link to the pre-survey assessing pain and mood as well as paper versions of the survey. [name] will provide an engaging overview of the three available kits, and patients will select a kit to try for the in-person workshop. [name] and the Study Coordinator will be present to provide Spanish translation and explanation as necessary. The last 15 minutes of the workshop will be saved for patients to complete the post-survey on pain and

mood and to remind patients that they will be compensated for using the art kits at home up to four (4) times if they complete pre- and post-surveys. Finally, patients will be informed that they will be invited to bring their artistic outputs to be photographed by a professional photographer ([name]) at the end of the four-month period and to share their experiences of making the art, so that they can share what they have made with the broader community. It will be made it clear that displaying their art and sharing their experiences is not mandatory, that patients do not need to decide during the workshop if they will want to share their artwork, and that they will be able to use full, part, or none of their name in the event.

At-Home Artmaking: Patients will be invited to take home all three (3) art kits at the end of the in-person workshop, each of which will allow them to make multiple versions of the type of art in question (aka materials for multiple mandalas). Each kit will include multiple copies of the pre- and post-survey assessing pain and mood and a reminder to complete the pre- and post-survey when doing the kits to receive an incentive of \$20 compensation for up to four (4) times within a four-month period (the end date will be included in the art kits). Communication from the Survey Coordinator will also include the links to the pre- and post-surveys. The instructions will prompt patients to complete the survey immediately before starting the art kit and immediately after concluding. Patients will further be prompted to include a photo of their art in the post-survey if they are using the online survey system, or they can text their photo to the Study Coordinator if they have phone-based photography capacity. All instructions will be in English and Spanish. This implementation process is designed to assess real-world use of the art kits.

Data Collection:

Event	Data Collection Method	Measures to be Collected
In-Person Workshop	Patients complete online pre- and post-survey via a QR code or paper form	
 • Questions 1-3 of the BPI Reduced Minus Peg Questions (pre) and question 3 of the BPI Reduced Minus Peg Questions (post) • Pain Catastrophizing Questionnaire • Single question asking about current level of depression • Single question asking about current level of anxiety • IOS-CC • Questions asking about current and recent unprescribed opioid use (pre) and level of highness in the moment (pre, post) • Single question asking about experience with art • Single question asking about openness to mindfulness activities
At-Home Artistic Practice #1	Patients complete paper pre- and post-survey	
 • Questions 1-3 of the BPI Reduced Minus Peg Questions (pre) and

At-Home Artistic Practice #2		question 3 of the BPI Reduced Minus Peg Questions (post) 
 • Single question asking about current level of depression • Single question asking about current level of anxiety • IOS-CC • Questions asking about current and recent unprescribed opioid use (pre) and level of highness in the moment (pre, post)
At-Home Artistic Practice #3		
At-Home Artistic Practice #4		
Check-in Texts & Calls	The Study Coordinator will text all patients one (1) month after the in-person workshop and every one (1) month thereafter for a total of four (4) connection points to assess any barriers to at-home engagement; for those patients who do not respond to texts, the Study Coordinator will complete phone calls and document in Redcap	
 • Question asking whether patients used the art kits in the past month • Documentation of any barriers • Brief qualitative data
Meaning Making Session	All patients will be invited to join a two-hour virtual meaning making session	
 • Rich qualitative data of their experience of the art kits and solo repetitive artmaking
Exhibit	Exhibit viewers (laypersons) will complete an online post-survey via QR code that captures reactions before/after viewing the exhibit	
 • Short set of stigma questions to be developed

Most data will be collected online, via an online survey that automatically populates into a password protected spreadsheet. The Patient Advocate or Study Coordinator will collect all paper surveys during routine treatment at [name] and provide them to the Study Coordinator, who will clean and manually input the data.

Data Analysis:

Analysis will be conducted through a mixed-methods approach. Quantitative analysis to test hypotheses 2-5 will be led by [name], Biostatistician, who will report changes from pre- and post-surveys on all the measures provided to patients and exhibit viewers. For bivariate analyses, he will use paired t-tests. For multivariate analyses, he will employ control variables from baseline, such as demographic variables, and conduct linear regressions. Qualitative analysis to test hypotheses 1-5 will be led by the co-PI, who will code all qualitative data collected from patients (open-ended questions in all surveys, transcript from the meaning making session) to

surface themes that can provide phenomenological or experiential data. Drs. [name] and the co-PIs will collaborate to develop a final report that includes both quantitative and qualitative data.

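### Hypothesis 6 concerns laypersons, but the exhibit is on the Montefiore campus and no step or survey item identifies which viewers are lay

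*Combined protocol and SAP*

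**What the plan says.** **Target.** In section 1, Aim 3 is to prepare the exhibit and "evaluate whether this exhibit impacts stigma regarding chronic pain and opioid use in the broader population (audience"). The criterion for Hypothesis 6 reads: "Laypersons who view the exhibit and who complete a retroactive pre-post survey will self-report lessened stigma".

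**Venue.** The Overview in section 3 says "Photographs and stories will be shared on the Montefiore campus as an art exhibit". The same section says that the patients are recruited "from a Montefiore-led methadone clinic". No other venue is named.

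**Respondents.** The Overview says that "the layperson audience will be surveyed to assess any resultant alteration in feelings of stigma". The Data Collection table says "Exhibit viewers (laypersons) will complete an online post-survey via QR code". The term layperson is not defined, and the eligibility criteria in section 4 are for patients only.

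**Data and analysis.** The only viewer measure in the table is: "Short set of stigma questions to be developed". Under Data Analysis, the biostatistician will "report changes from pre- and post-surveys on all the measures provided to patients and exhibit viewers". No split of the viewers is mentioned, and the hypotheses assigned to quantitative testing are 2 to 5, so Hypothesis 6 is not among them.

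**The concern.** The hypothesis is about one population, and the sampling frame probably yields a mixture. An exhibit on the campus of the institution that leads the methadone clinic will plausibly draw clinicians, other staff and trainees as well as outside visitors. Section 5 adds that the co-PIs present the project to staff at scheduled meetings, so some staff will already know of it. These people are not laypersons in the ordinary sense, and their attitudes to chronic pain and opioid use may start from a different level and move differently.

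If the survey holds only stigma items, the report of Aim 3 will credit the reaction of whoever responded to the public. A real change in laypersons could be diluted, or a change confined to staff could be read as a change in public stigma. Once the exhibit has closed, a respondent's role cannot be recovered from stigma answers.

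**Working it through.** The plan gives no sample size, power, effect size or audience mix for Hypothesis 6, so there is no figure to reproduce. The check has two parts.

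**1. The sections side by side**

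| Element | Where | Content |
|---|---|---|
| Population of interest | Section 1, Aim 3 and Hypothesis 6 | Laypersons, broader population |
| Place of sampling | Section 3, Overview | Montefiore campus only |
| Respondent label | Section 3, Overview and Data Collection table | Audience or viewers described as laypersons |
| Definition or screen for lay status | None | None; section 4 covers patients |
| Viewer variables | Section 3, Data Collection table | Stigma questions only |
| Split in the analysis | Section 3, Data Analysis | None |

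Patients, by contrast, give demographics, experience with art and openness to mindfulness at the workshop. Nothing comparable is listed for viewers, so no listed variable could define a lay subset.

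**2. Illustration on assumed values**

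Let s be the share of non-lay respondents, and d_lay and d_other the mean changes in SD units. The change averaged over all respondents is

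(1 − s) × d_lay + s × d_other.

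None of these inputs is in the documents. The illustration takes 0.5 SD in one group and 0 in the other, with s from 25% to 75%.

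| Share non-lay | Only laypersons change (0.5, 0) | Only others change (0, 0.5) |
|---|---|---|
| 25% | 0.75 × 0.5 = 0.375 | 0.25 × 0.5 = 0.125 |
| 50% | 0.50 × 0.5 = 0.25 | 0.50 × 0.5 = 0.25 |
| 75% | 0.25 × 0.5 = 0.125 | 0.75 × 0.5 = 0.375 |

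The two columns coincide only at 50%; elsewhere they run in opposite directions. As s is not recorded, an observed average of, say, 0.375 SD fits a mostly lay audience that changed or a mostly non-lay one that changed.

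For the second column, suppose that a two-sided 5% paired test were applied to all respondents. With n viewers, the chance of a significant result although laypersons did not change is about

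Φ( 0.5s × √n / √(1 + 0.25 × s(1 − s)) − 1.96 ).

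For n = 100 and s = 50%, this is Φ(2.5 / 1.031 − 1.96) = Φ(0.465) = 68%.

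| Share non-lay | n = 50 | n = 100 |
|---|---|---|
| 25% | 14% | 23% |
| 50% | 40% | 68% |
| 75% | 74% | 96% |

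**Benign case.** If both groups change by 0.3 SD, the average is 0.3 SD at every share and pooling does no harm.

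**The case against.** The strongest reply is that the mixed audience is not documented. The plan does not say who will visit, how the exhibit will be publicised, or which part of the campus will be used. The Overview and Hypothesis 6 can also be read as limiting the survey to laypersons. That stands: a reader might infer that every viewer is counted as a layperson, and the text does not go that far. What remains is narrower. On either reading, no step or item identifies who is lay.

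A reader might also infer that artists' relatives, or viewers with chronic pain or opioid use disorder (OUD), contaminate the sample. The documents do not support this. Such people are ordinarily laypersons and belong to the broader population; section 2 puts chronic pain at about 20-21% of US adults. Dropping them from the main analysis would change the hypothesis. Because Hypothesis 6 is judged partly by appraisal of the artists, and artists may show their names, personal acquaintance merits a sensitivity analysis but not exclusion.

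It is fair, too, that the SD figures are assumed, that no test of Hypothesis 6 is specified for mixing to distort, and that this is a secondary focus of an exploratory pilot. These points limit the weight of the concern. They do not supply the missing link between the respondents and the stated population.

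**Conclusion.** The concern holds in a limited form. As written, a change in stigma among respondents could not be attributed to laypersons, and still less to the broader population, because the venue makes a mixed audience likely and the listed data cannot separate its parts. The size is unknown. The averages of 0.125 to 0.375 SD show what mixing could do under assumed effects and shares; they do not estimate what will happen in this study.

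It would be too strong to conclude that Aim 3 cannot be answered or that the damage is fixed. The viewer questions are still to be developed, so the gap can be closed before any data are collected. Mixing is also harmless if nearly all viewers are lay or if both groups change alike. The conclusion rests on one inference, that staff or trainees will be among the respondents. This should be changed before the exhibit survey is finalised.

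**What to change.** While the survey is being written:

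- **Add one role item:** Montefiore, health-care or clinic staff or trainee; study participant; visitor or other. Optionally, add one item on whether the viewer knows an exhibiting artist.
- **Define the Hypothesis 6 set in the Data Analysis section:** viewers who are not health-care or clinic staff or trainees and not study participants. Report the other groups separately. Naming Hypothesis 6 there would also close the related gap that it is assigned to no quantitative analysis.
- **Keep relatives and people with chronic pain or OUD in the lay set.** If the second item is used, add a sensitivity analysis excluding viewers who know an artist.
- **Do not ask viewers about their own OUD.** That is sensitive health information, and the confidentiality provisions in sections 7 and 8 are written for patients.
- **Limit the conclusion** to campus exhibit viewers who chose to respond. A role item does not make campus visitors represent the broader population.

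The cost is one or two extra items and a smaller analysis set. With 100 respondents and the assumed non-lay shares of 25% to 75%, 100 × (1 − s) leaves 75 to 25 viewers for Hypothesis 6.
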